### 2.4. Definition of Subgroups

Subgroup analyses will be performed for participants who will receive delayed (due to COVID-19 pandemic) Dose 2 vaccination:

- If more than 10% of participants in the immunogenicity subset receive their second vaccination outside the widened (ie,  $-3/+28$  days) window (as defined in CTP Amendment 3) of Day 57, then the immunogenicity analysis will be performed to evaluate the potential impact of delayed (ie, outside the widened window) Dose 2 vaccination on the immune response.
- Similarly, if more than 10% of all participants receive their second vaccination outside the widened window (as defined in CTP Amendment 3), then analysis will be performed to evaluate the potential impact of delayed (ie, outside the widened window) Dose 2 vaccination on safety measures.

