Depending on the extent of the COVID-19 impact on the study, additional participants will be recruited in the immunogenicity subset. For instance, shortly after participants received Dose 1 vaccination, “stay-at-home” orders were imposed in the areas where the sites were located. Although the sites had implemented appropriate safety measures to prevent spread of SARS-CoV-2, approximately 22% of participants did not return to the site within the original protocol-defined windows ( $\pm 3$  days) for Dose 2 administration. Investigators were then instructed to bring participants back to the site to complete the vaccine regimen, even if they were out of window. Currently, the “stay-at-home” orders have been lifted and some

participants are returning to the sites for follow-up. In order to reduce the number of additional participants needed for the primary and secondary immunogenicity analyses without jeopardizing the evaluation of the primary and secondary objectives of the study, the window around Dose 2 administration for the main part of the study (Groups 1-4) was widened in CTP Amendment 3. In particular, the upper limit of the window around Day 57 (Dose 2) was extended to Day 85 (ie, Day 57+28 days). The widening of window was deemed acceptable after examination of the immunogenicity data from previous studies (ie, VAC52150EBL2001 and VAC52150EBL2002) in which Dose 2 was administered at intervals  $\geq$ 56 days. Although there appears to be a trend of increasing GMCs with increasing intervals between Dose 1 and Dose 2 from those studies, the variability (standard deviation) of the immune responses (binding antibody levels against the EBOV GP using ELISA [EU/mL]) remains stable and in line with the currently assumed standard deviation of 0.55 (on the log10-scale). Assuming that the delayed Dose 2 administration will be randomly distributed among the groups (ie, Groups 1-4), widening the acceptable time frame to administer Dose 2 by increasing the upper limit of the window to 28 days (ie, Day 57+28 days) is not expected to adversely affect the primary and secondary objectives of the study. See CTP Amendment 3 for further details. Unless otherwise mentioned in this document, the “protocol-defined window” refers to the visit windows as defined in CTP Amendment 3.

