### 2.3.2. Per Protocol Analysis Set

The per protocol analysis set for the main part of the study (Groups 1-4) will include all randomized and vaccinated participants, who received both Dose 1 and Dose 2 vaccinations (administered within the protocol-defined window), had at least one postvaccination (ie, after the date of vaccination) evaluable immunogenicity sample, and had no major protocol deviations that may influence the immune response. Similarly, the per protocol analysis set for the Booster Cohort (Groups 5-6) will include all vaccinated participants, who received Dose 1, Dose 2, and the booster vaccination (ie, both Dose 2 and booster vaccination within the protocol-defined window), had at least one postvaccination (ie, after the date of vaccination) evaluable immunogenicity sample, and had no major protocol deviations that may influence the immune response.

Note that the per protocol analysis set will only be defined for participants included in the immunogenicity subset and the booster cohort. The following will be considered for the immunogenicity analysis based on the per protocol analysis set:

- The primary and secondary hypotheses will be based on those in the set with data at 21 days post Dose 2 and 56 days post Dose 1, respectively. Participants who will receive incorrect batch (other than the one randomized to) of vaccination will only be excluded from these hypothesis tests.
- Immunogenicity samples obtained after missed doses (or out-of-window Dose 2 or Dose 3 vaccinations), samples obtained after natural infection (if applicable), or samples obtained outside the protocol-defined window will be excluded in graphs and tables showing descriptive statistics. These measurements will however be shown in listings, together with the indication that they are not used in the analysis.
- If more than 10% of participants from the full analysis set are excluded from the per protocol analysis set, then the immunogenicity analysis (including both primary and secondary hypothesis testing) will be repeated on the full analysis set to evaluate the robustness of the analysis results.

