#### **4.3. Vaccination Compliance**

The number and percentage of participants receiving the second vaccination within (and outside) the  $\pm 3$  days and  $-3/+28$  days windows will be summarized. Also, a summary and/or listing of participants who missed second vaccination or received it outside the protocol-defined window due to the COVID-19 pandemic will be generated.

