### ***Other Analysis***

The secondary objective will be assessed similar to the primary objective, but at 56 days post Dose 1. Equivalence of the 3 different lots of Ad26.ZEBOV (Lots A, B, and C) will be established if equivalence is shown for all 3 pairwise comparisons (Lots A vs B, A vs C and B vs C) at 56 days post Dose 1.

As sensitivity analyses to the widened window around Dose 2 administration for the main part of the study (Groups 1-4) under CTP Amendment 3, both the primary and secondary hypotheses will also be tested as sensitivity analysis based only on data of participants who received the second vaccination within the original (ie,  $\pm 3$  days) window around the Day 57 visit.

The following outputs will also be generated and presented by vaccination groups:

- Table of summary statistics (including geometric means and corresponding 95% CIs, geometric mean fold increase [from Pre-dose 1, Pre-dose 2 and Pre-booster] with corresponding 95% CI), responder rates and positive sample interpretation (ie, showing number, percentage and the exact 95% Clopper-Pearson CI) at all available time points.
- Dot plots (on a log10-scale) with distinction between positive and negative sample interpretations at all available time points.
- Graphic (on a log10-scale) of regimen profiles (ie, geometric mean concentrations with 95% CIs over time).
- Reverse cumulative distribution curve using binding antibody concentrations (log10-scale) by percent of participants with antibody concentrations at baseline and each post-baseline visit time point.
- Data listing.

To evaluate the potential impact of delayed (ie, outside the widened window due to COVID-19 pandemic) Dose 2 vaccination on the immune response, the following additional outputs will be generated (only if more than 10% of participants in the immunogenicity subset receive delayed [ie, outside the -3/+28 days window around Day 57] Dose 2 vaccination) for the binding antibody concentrations and presented for participants having received Dose 2 vaccination within the -3/+28 days window around the Day 57 visit (as defined in CTP Amendment 3) window versus those having received Dose 2 outside that window:

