- Table of summary statistics (including geometric means and corresponding 95% CIs, geometric mean fold increase [from Pre-dose 1 and Pre-dose 2] with corresponding 95% CI), responder rates and positive sample interpretation (ie, showing number, percentage and the exact 95% Clopper-Pearson CI) at all available time points.
- Dot plots (on a log10-scale) with distinction between positive and negative sample interpretations at all available time points.
- Scatter plot of the 21 days post Dose 2 immune response versus the elapsed time (days) between Doses 1 and 2 vaccinations.

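### Should the delayed-Dose-2 immunogenicity outputs show participants dosed at +4 to +28 days separately, and be produced without the 10% trigger?

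*SAP*

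**What the plan says.** Amendment 3 extended the upper limit of the Dose 2 window for Groups 1-4 from Day 60 to Day 85. SAP 1.2 gives the reason: "approximately 22% of participants did not return to the site within the original protocol-defined windows" of ±3 days. It adds a caveat, "Although there appears to be a trend of increasing GMCs with increasing intervals between Dose 1 and Dose 2 from those studies", and reports that the spread stayed stable. It then assumes that delay is spread at random over the groups.

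The SAP handles Dose 2 timing in three places.

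- **Re-test (2.3.2 and 6.3.1, Other Analysis).** Without any condition, "both the primary and secondary hypotheses will also be tested as sensitivity analysis based only on data of participants who received the second vaccination"; here this means a second dose inside the old ±3-day limits.
- **Compliance (4.3).** "The number and percentage of participants receiving the second vaccination within (and outside) the" ±3-day and −3/+28-day windows will be summarised.
- **Delay outputs (2.4 and 6.3.1).** These run only under a condition: "If more than 10% of participants in the immunogenicity subset receive their second vaccination outside the widened" window. When they run, they are "presented for participants having received Dose 2 vaccination within the -3/+28 days window around the Day 57 visit", set against those dosed outside it. They include the "Scatter plot of the 21 days post Dose 2 immune response versus the elapsed time (days) between Doses 1 and 2 vaccinations", which appears nowhere else.

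SAP 2.3.2 also has a rule for per protocol descriptive tables and graphs. Among the samples it leaves out are these: "Immunogenicity samples obtained after missed doses (or out-of-window Dose 2 or Dose 3 vaccinations"). Section 6.3.1 does not name the analysis set for the delay outputs.

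**The concern.** The participants whose admission Amendment 3 had to justify are those dosed on Days 61 to 85. In the delay outputs they share a column with participants dosed on time, whether or not the trigger fires. The trigger also tends to stay silent when the amendment works: each participant brought back by Day 85 no longer counts towards the 10%, and participants who never receive Dose 2 do not count either. So the trial could hold direct evidence on the interval effect and not display it, although the plan itself expects GMCs to rise with the interval.

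A second worry is that, under the per protocol rule on out-of-window samples, the post-Dose 2 outside-window column would be empty.

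If late dosing raised antibody levels and fell unevenly across lots, a lot ratio could be shifted, and the reader would want to see that.

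**Working it through.** **Inputs.** From SAP 1.4: SD 0.55 on the log10 scale, true ratio 0.9, margins 0.5 and 2.0, 5% dropout, 144 per active group. From SAP 1.2: immunogenicity subset 456 (432 active plus 24 placebo), and 22% outside ±3 days. Assumed here: the 22% applies to the subset. Also assumed, because the documents give no size for either: a late/on-time GMC fold of 1.25 to 2.0, and the imbalance in lateness between lots.

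**1. The plan's own figure.** The power of two one-sided tests at 2.5% each with 136 per group (144 × 0.95 = 136.8) is 96.75%, against the stated 96.55%. The overall figure follows from 0.9655³ = 0.900. The inputs reproduce.

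**2. When the trigger fires.** 10% of 456 is 45.6, so 46 participants are needed. Outside ±3 days: 0.22 × 456 = 100.3. Share of these who must be dosed outside −3/+28: 46/100.3 = 46%. If 5% (22.8) are never dosed and are part of the 22%, it is 46/77.5 = 59%. The trigger may well stay silent; that part of the concern is right.

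**3. What the re-test keeps.** On time per group: 0.78 × 144 = 112. Power for the pair at ratio 0.9 is 93%. Joint power over the three pairs, by simulation, is 86-87%. With a further 5% lost (107 per group) the figures are 92% and 84-85%.

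**4. Recovering the late-in-window GMC.** Both windows start at −3 days, so the per protocol set is the on-time participants plus those dosed at +4 to +28 days. The analysis of variance has group as its only term, so each group's estimate is the mean of log10 values. With W for the widened window, O for on time and L for late:

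mean_L = (n_W × mean_W − n_O × mean_O) / (n_W − n_O)

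All four quantities come from planned analyses, by lot, at 21 days post Dose 2 and likewise for the pre-Dose 2 sample. The change in n by lot also shows whether lateness is balanced. SAP 4.3 gives the counts for both windows, and Section 4 presents data by group as its general rule. Individual values go into the data listing in 6.3.1.

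**5. The empty column.** The exclusion in 2.3.2 is stated for per protocol analyses. SAP 2.1 gives the other rule: in full-analysis-set analyses, assessments outside the windows are kept. A comparison of inside with outside the window cannot be a per protocol analysis, so an analyst would use the second rule.

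**6. Possible shift in a lot ratio.** Shift = fold^(difference in late share).

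| Fold | 5 points | 10 points | 22 points |
|---|---|---|---|
| 1.25 | 1.011 | 1.023 | 1.050 |
| 1.5 | 1.020 | 1.041 | 1.093 |
| 2.0 | 1.035 | 1.072 | 1.165 |

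The CI half-width factor at 137 per group is 10^(1.96 × 0.55 × √(2/137)) = 1.35. Take the worst cell acting against the assumed ratio: 0.9/1.165 = 0.77, with a lower limit near 0.77/1.35 = 0.57. That is still above 0.5.

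**7. What a separate column would deliver.** For Groups 1-3 pooled, with 337 on time (0.78 × 432), the CI factor is 10^(1.96 × 0.55 × √(1/n_L + 1/337)).

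- Everyone late is dosed by Day 85: n_L = 95 gives 1.33. With 5% never dosed, n_L = 73 gives 1.38.
- Trigger silent with 45 dosed outside the widened window: 55 or 32 remain of 456, about 52 or 30 in Groups 1-3, giving 1.45 or 1.60. Per group (about 17 or 10 against 112) it is 1.90 or 2.26, about as wide as the equivalence margin.

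The 55 and 32 are not lower bounds, because the number never dosed is not in the documents. With 40 never dosed, 100 − 40 − 45 = 15 remain.

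**The case for a change.** The strongest case for changing the plan is that the widening rests on other studies' data and an assumption, while this trial can look directly at little cost. Three interval categories and one unconditional plot need no new data, test or model, and fixing them before unblinding avoids a post hoc table. The secondary endpoint adds weight. The sample labelled 56 days post Dose 1 is the pre-Dose 2 sample, so for late-in-window participants it is drawn 60 to 84 days after Dose 1, and the plan's argument about the dose interval does not discuss that.

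Much of this stands as fact. There is no +4 to +28 day column, the plot is conditional, the set for the delay outputs is not named, and the later pre-Dose 2 sampling is real. Removing late participants in the re-test is not the same as describing them.

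What does not follow is that the cut-off is wrong. The SAP uses two tools for two questions: the ±3-day re-test for participants admitted by the amendment, and the conditional subgroup for those dosed outside even the widened window. The re-test also covers the secondary hypothesis. The pooled late-against-on-time contrast is the more precise part of the addition, but it says nothing about lot consistency, since an effect shared by the lots cancels. It is also not a randomised comparison. The per-lot version, which would bear on consistency, is too imprecise to read.

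**Conclusion.** No change to the plan follows. This is a fair choice of reporting with one unnamed analysis set, which SAP 2.1 lets analysts fill sensibly: the full-analysis-set rule, restricted to immunogenicity-subset participants with the sample. Followed as written, the plan still gives a sound lot-consistency conclusion. The unconditional re-test has about 93% worst-pair and 86-87% joint power. A 10-point imbalance in lateness moves a lot ratio by a factor of 1.02 to 1.07 against a 2.0 margin, and even the extreme cell (1.165) leaves the expected limit inside the margin at the planned ratio of 0.9. The late-in-window GMC can be derived by lot from planned results.

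The sponsor may choose to show the scatter plot regardless of the trigger and add a descriptive late-in-window category. That would help a reader, but would not alter any estimate, test, bias or power.

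The figures assume that the 22% applies to the immunogenicity subset, that the SD of 0.55 holds, and that the late/on-time fold lies between 1.25 and 2.0. The documents do not give the fold or the number never dosed.

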## 3. INTERIM ANALYSIS AND DATA MONITORING COMMITTEE REVIEW

The current SAP is applicable to the primary, interim and final analyses:

- The primary safety and immunogenicity analyses will be performed when all participants in Groups 1-4 have completed the 28-day post Dose 2 visit or discontinued earlier, and the database is locked. This analysis will include all available data up to this point. Only sponsor personnel not involved in the review and determination of causality of serious adverse events (SAEs) reported during the study

will be unblinded to Groups 1-4 at this time point.

- An interim analysis will be performed when all participants in Groups 1-4 have completed the 6-month post Dose 2 visit, ie, the last study-related visit (or discontinue earlier), and the database has been locked.
- For the Booster Cohort (Groups 5-6), an interim analysis will be performed when all participants in Groups 5-6 have completed 28-day post booster dose time point (or discontinued earlier). This analysis, based on the corresponding locked database, will include all available data (including safety and 21-day post booster dose immunogenicity data) up to the cut off. Only sponsor personnel not involved in the review and determination of causality of SAEs reported during the study will be unblinded to Groups 5-6 at this time point.
- The final analysis will be performed when all participants in the study have completed the last study-related visit or have discontinued earlier (and the database is locked).

A planned analysis may be combined with the subsequent analysis, if deemed necessary (eg, when the dates of 2 planned database locks are very close). The study is considered completed when the last participant has completed the last study procedure.

A multidisciplinary Safety Management Team (SMT) is in place for the development of the Ebola vaccine regimen. This SMT will monitor the safety of the participants in this study as part of its regular surveillance of all clinical studies using the Ebola vaccines Ad26.ZEBOV and MVA-BN-Filo. Refer to CTP Section 9.3 for details.

## 4. SUBJECT INFORMATION

Participant information will be shown for the full analysis set. In general, the data will be presented by vaccination group.

### 4.1. Demographics and Baseline Characteristics

Demographic and screening/baseline characteristics will be tabulated and summarized with descriptive statistics per vaccination group (as shown in Table 2) and over all participants. The following demographic and baseline characteristics will be summarized:

- Sex (Female/Male)
- Age (years)
- Race
- Ethnicity
- Height (cm)
- Weight (kg)
- Body mass index (BMI, kg/m^2), calculated from the recording of baseline height and weight
- Baseline EBOV-GP binding antibody (EU/mL) positivity, only for the immunogenicity subset and the booster cohort
- Positivity of baseline viral neutralizing antibody (VNA) against the Ad26 vector (IC90 titers), only for the booster cohort

### 4.2. Disposition Information

The number and percentage of participants screened, participants in the full analysis set, participants vaccinated but not randomized, participants randomized but not vaccinated, participants who completed

(study completion and vaccination completion) and discontinued participants (study discontinuation and vaccination discontinuation) with the reason of discontinuation will be tabulated per vaccination group and overall. Also, the number of participants and percentage in each analysis period will be tabulated.

#### **4.3. Vaccination Compliance**

The number and percentage of participants receiving the second vaccination within (and outside) the  $\pm 3$  days and  $-3/+28$  days windows will be summarized. Also, a summary and/or listing of participants who missed second vaccination or received it outside the protocol-defined window due to the COVID-19 pandemic will be generated.

#### **4.4. Protocol Deviations**

Major protocol deviations will be summarized by deviation category. A listing of the major protocol deviations will also be generated. The deviations that have the potential to influence immune response will be flagged in the listing. In addition, all COVID-19 related protocol deviations (ie, both major and minor deviations) will be summarized and/or listed.

#### **4.5. Concomitant Medications**

The analysis of concomitant therapies will be done using the World Health Organization (WHO) drug coded terms. If the coded term for a concomitant medication is missing, then the reported term will be used and flagged in the table. The concomitant therapies will be tabulated per analysis period. Additionally, a listing of all pre-study and concomitant therapies will be provided. There will be special attention to analgesics/antipyretics (such as acetaminophen, non-steroidal anti-inflammatory drugs [NSAIDs] and aspirin) administered during the first 8 days (including the day of the vaccination) following each vaccination. Special attention will also be given to all COVID-19 related concomitant therapies, if applicable.

Based on their start and stop date, concomitant therapies will be reported in each applicable analysis period. If a concomitant therapy record misses components of its start and/or stop dates (day and/or month and/or year), then they will be assigned as follows:

- In case of partial start or stop dates, the concomitant therapy records will be allocated to periods using the available partial information, without imputations. If, for example, only month and year are available, these will be compared to the month and the year of the periods, and the concomitant therapy record will be allocated to the period(s) where these date parts match. This rule may lead to assignment to multiple periods.
- In case of a completely missing start date, the concomitant therapy will be considered as having started before the trial.
- In case of a completely missing end date, the concomitant therapy will be considered as ongoing at the end of the trial.

**Remark:** In addition to the date information, time information will be considered to allocate concomitant therapies to analysis periods, if available.

### **5. SAFETY**

Safety analyses will be performed on the full analysis set. Frequencies and percentages (one decimal place) will be generated for the AEs. No formal comparisons between groups will be provided.

The safety data will be presented by vaccination group (as shown in [Table 2](#)). The data will be presented by analysis period (post-dose 1, post-dose 2, and post-booster [only for the booster cohort]) as well as over the entire regimen period (ie, combined post-dose 1 and post-dose 2 periods, and combined post-dose 1, post-dose 2 and post-booster [only for the booster cohort]). Denominator for the percentages will be the

number of participants in the considered analysis set and period/phase for a certain vaccination group (eg, incidence per 100 participants/period).

To evaluate the potential impact of delayed (due to COVID-19 pandemic) Dose 2 vaccination, safety data will also be presented (only if more than 10% of participants receive Dose 2 vaccination outside the widened window) for participants having received Dose 2 vaccination within the widened window (as defined in CTP Amendment 3) versus those having received Dose 2 outside the window.

